### **3. RESEARCH METHODS**

#### **3.1 Study Design**

This will be a pragmatic, cluster randomized clinical trial comparing the effectiveness of two different oral nutritional supplement protocols and accompanying education. All participants in participating facilities will be asked to participate in the study unless they do not qualify. Reflecting the pragmatic study design targeting broad generalizability, inclusion criteria are broad and exclusions are minimal.

### **3.2 Intervention**

#### **1. Usual Care versus Intensive Protocols**

Facilities will be cluster randomized into one of two protocols:

- a. Usual care protocol which will continue the current nutritional supplement protocol for all patients at the dialysis facility, whereby those with albumin below 3.5 g/dL receive supplement
- b. Intensive nutritional supplement protocol, which will prescribe nutritional supplements for all patients at the dialysis facility regardless of serum albumin levels

The majority of DCI facilities currently have the majority of their patients prescribed the usual care oral nutritional supplement protocol, with 20-30% of patients at any given time receiving an in-center oral nutritional supplement. Of note, all patients are offered the protocol, but approximately 10-20% refuse the protein supplement, often due to taste and individual preference. Being prescribed the protocol does not affect a patient's ability to consume food or other supplements of their choosing before, during (depending on facility and state regulations) or after dialysis; it simply means that they receive an oral nutritional supplement for consumption during dialysis from the dialysis facility included as a part of their routine dialysis care. The specific nutritional supplement is not specified in the protocol, although many facilities currently use Prostat due to pricing and availability. The protocol prescribes approximately 15 g of oral protein supplement; when Prostat is used, this is accomplished by drinking 30 mL of Prostat. In cases of facility or patient preference, including taste fatigue, other supplements can be used in the current usual care protocol in lieu of Prostat (as was the case in the quality improvement report published by Lacson and colleagues). For example, the PI's facility currently has some patients receiving Prostat while others receive BodyQuest Protein Ice Cream, reflecting patient preference. Nutritional supplements utilized during the trial will vary, but should contain approximately 15 g (range 12 to 20 g) of protein with low sodium, potassium and phosphorus content. Based on current use within DCI and availability as well as prior experiences and cost, we anticipate the following protein supplements will be utilized:

- a) BodyQuest Protein Ice Cream, which contains 16 g of protein and 120 kcal per serving
- b) Prostat, Sugar Free, which contains 15 g of protein and 100 kcal per serving
- c) LiquaCel Liquid Protein, which contains 16 g of protein and 90 kcal per serving
- d) ZonePerfect Nutrition Bars ( flavor varied to avoid taste fatigue), which contain ~ 15 g of protein and ~ 210 kcal per serving
- e) Nepro, which contains 19 g of protein and 425 kcal per serving.

## 2. Implementing the Intervention

As occurs currently in practice, the serum albumin level from routinely drawn monthly labs will automatically feed into the electronic centralized nutritional supplement prescribing protocols, from which supplements are then prescribed and administered. The DCI electronic oral nutritional supplement protocol will be used in the same manner as in current practice and follow the same rules for dosing and stoppage for the usual care arm, while protocol-based administration will continue regardless of serum albumin level for the intensive protocol arm. All new patients at the time of dialysis initiation (first dialysis session) will receive an oral nutritional supplement if prescribed the protocol by their physician. The specific supplement is typically based upon what the individual facility has available and on storage space within facilities. For example, one supplement is a frozen protein supplement (BodyQuest Protein Ice Cream) that can only be used in facilities that have adequate space for food freezers.

As a non-blinded study, the treating physicians will be aware of the study allocation of the facility. In facilities assigned to the intensive oral nutritional supplement intervention, an order will be generated in the DCI MIS by DCI Information Services for administration of an oral protein supplement at each dialysis session. Similarly, in patients assigned to the standard oral nutritional supplement intervention, a renewal order of the current supplement protocol will be generated. As with all orders pertaining to in-center hemodialysis care, the order for intensive versus standard nutritional supplement protocol will need to be signed electronically by the physician caring for the patient. If the physician does not sign this order, the patient will not receive nutritional supplements. The physician, regardless of randomization, can elect to discontinue the supplement order at any time.

As is currently done in practice, the dialysis nurse will record in the treatment record that the nutritional supplement has been dispensed and whether and when it was consumed. Supplements should be distributed and consumed within the first 30 minutes of initiation of a dialysis session.

### **3.3 Facility and Patient Education Efforts**

Within all facilities, patients will receive information regarding the nutritional supplement trial. These are described in further detail below. Educational posters will be displayed in public waiting areas, including signs and posters that inform patients that the site is participating in the trial as

well as signs and posters that promote the importance of nutrition and adequate protein intake in recipients of hemodialysis. Every dialysis facility, as a condition for coverage by CMS, is required to have a dietitian who provides nutritional information to patients. Regardless of randomization assignment, this individual will continue to encourage appropriate protein intake for dialysis patients, including recommendations for protein and other hemodialysis-appropriate diet consumption at home.

Facilities randomized to usual care and to intensive supplements will have slightly different approaches. First, facilities randomized to the usual care arm will have different signs and posters than those randomized to the intensive arm. Usual care arm materials will promote the need for nutrition and encourage supplement consumption when the albumin is low. Patients are informed of their serum albumin levels monthly at dialysis when they receive feedback from the dietitian. In these conversations, the dietitian will continue to emphasize protein consumption as per prior routine. For intensive facilities, materials will focus on the catabolic stresses induced by dialysis regardless of baseline albumin level, and emphasize that oral nutritional supplements taken early during dialysis may be able to impact catabolism. Reflecting the open nature of dialysis facilities, if neighboring patients are on different treatment regimens, they are likely to overhear the specific counseling given to other patients and are likely to appreciate that others are receiving more or less supplements than they are. Finally, there is a group mentality prevalent among dialysis patients such that they expect to receive similar treatment and interventions. These factors reinforce the hemodialysis environment as best suited to cluster randomization.

### **3.4 Blinding**

Patients, investigators, and dialysis unit physicians and staff will not be blinded to study arm assignment. The endpoints committee will be blinded to facility (and therefore patient) treatment assignment.

### **3.5 Eligibility**

To maintain broad generalizability and the pragmatic nature of the trial, eligibility and exclusion criteria are minimal and based largely on common sense. The following criteria will identify potential study participants:

#### **1. Inclusion Criteria**

- a. Receipt of in-center hemodialysis in a facility participating in the trial
- b. Able to consume oral nutritional supplements
- c. Age  $\geq 18$  years

#### 2. Exclusion Criteria

- a. Tube feed or intravenous feed dependent
- b. Unable to feed oneself or request help with feeding if a supplement is provided
- c. Known allergy to ingredient(s) of the supplement

#### 3. Pregnancy

Pregnancy is rare in hemodialysis patients but pregnancy will not be an exclusion criterion as this is a minimal risk protocol and research has shown that protein supplements may actually be beneficial to the mother.

#### 4. Cognitively Impaired

Cognitively impaired patients will not be excluded as this is a minimal risk protocol and these patients' legally authorized representative will be asked whether they can be in the study.

#### 5. Racial and Ethnic Origin

DCI is a nationally representative dialysis organization, with dialysis clinics in 27 states across the US. Consistent with the racial/ethnic mix of the DCI population, we expect to enroll approximately 50-55% Caucasians, 40-45% African Americans, 5% Asians, and less than 5% of other racial background; 5% to 10% will likely be Hispanic. No racial / ethnic group will be excluded from participating.

#### 6. Other Vulnerable Subjects

Prisoners typically do not receive dialysis in any potential participating facilities, and, if this does occur, it is usually temporary until sentencing to a correctional facility where dialysis is available. Accordingly, prisoners will not be included in the trial.

### **3.6 Recruitment**

The study intervention is considered minimal risk given the nature of the intervention (roughly comparable to the amount of protein consumed with 2 large hard boiled eggs). To achieve

adequate power to evaluate mortality, we will need to recruit more than 5000 HD patients; this will require participation of more than 80 dialysis units throughout DCI, which nationally provides hemodialysis care to approximately 13,000 individuals. Given the pragmatic design of the trial, the high risk of cross-contamination between the usual care and the intensive intervention due to patient-patient interactions, other patient observed patient-dietician and patient-dialysis staff interactions, and our plan to promote the study to the entire facility, it is not practicable to conduct this research without a waiver of informed consent documentation.

Following education of facility staff, patients will receive study information sheets. Patients will have the opportunity to review the study information sheets and ask any questions they may have by contacting the study staff listed in the information sheets. Dialysis staff will note whether the patient agrees to be in the study by documenting it in their medical record. The process for initiating study sites is as follows:

- 1) Send the trial protocol to the governing body for each dialysis facility that is a potential trial participant. The governing body, which typically consists of the facility medical director(s), administrator, nurse manager(s) and chief technician, will review the protocol and have an opportunity to discuss the trial with the PI and central study personnel. Following this, they will need to approve of their facility's participation in the trial before their facility can be considered for inclusion.
- 2) Dialysis staff will participate in one to two pre-study conference calls, receive local facility materials such as posters and patient information sheets, and, at their discretion, have the opportunity to participate in study-wide conference calls that will occur monthly during the first several months of the trial before becoming quarterly thereafter.
- 3) All patients receiving dialysis in a participating facility prior to the start of the trial (but after the facility has been assigned randomly to a study arm) will receive an information sheet about the trial. These will be made available in multiple languages and will also be available to patient proxies. Information sheets and posters will also be posted in clinical areas of the dialysis facility. As with other information that is communicated to patients as a part of clinical practice, facility personnel will read forms to visually impaired or illiterate patients. All new patients who initiate dialysis at a participating facility will receive the information sheet that applies to their clinic at their initial treatment in the facility and will be asked whether they wish to participate

- 4) Patients can withdraw from the study at any time, regardless of intervention arm, by informing personnel at the dialysis unit that they do not want to take supplements or by simply not taking the supplement.

### **3.7 Trial Outcomes**

All trial outcomes are ascertained as a part of usual dialysis care and will not require additional efforts by the dialysis facility. Following randomization, facilities will remain in the study for three years. Trial outcomes are:

#### **1. Primary outcome**

All-cause mortality.

#### **2. Secondary outcomes:**

- a. Hospitalization rate
- b. 30-day re-hospitalization rate
- c. Infection, defined by a bloodstream infection, receipt of IV antibiotics in an outpatient DCI dialysis unit at three or more hemodialysis sessions, or hospitalization for a primary cause of infection
- d. Infection as defined by the above plus infection as a primary cause of hospitalization
- e. Serum albumin (in analyses exploring mediation if there is a benefit associated with the more intensive protocol)
- f. Economic analysis

#### **3. Outcomes Ascertainment**

Outcomes ascertainment balances the structure of a pragmatic trial with data needs for safety and effectiveness. In routine clinical practice, each facility reconciles events, including deaths, hospitalizations, and infections monthly. These clinical data will define outcomes in the study.

### **3.8 Randomization:**

Facilities will be randomized 1:1 to study arms, blocked by region and facility size (small, medium, large). If possible, randomization will occur concurrently for all participating facilities and with protocols available for prescribing immediately by physicians in the facility in the medical information system. Alternatively, depending on the time needed for facilities to approve the trial, we will randomize facilities over several months. Randomization will be performed by DCI's

Information Services (IS) personnel. DCI's IS personnel have experience with randomized clinical trials (RCTs), having designed and overseen an electronic algorithm that randomized patients to treatments arms across 3 strata in a past RCT conducted within DCI. They will create the master file of the treatment assigned to each facility. During the course of the trial, although facilities and patients and providers at those facilities will know their own randomization assignment, this information will not be made widely available to other dialysis units, physicians, patients, or staff, with the exception of the Data Safety Monitoring Board.

Approximately within four weeks following randomization, either treatment to usual care will be continued or treatment to the intensive protocol will begin depending on which protocol the unit has been assigned to as well as whether the patient agreed to be in the study. This gap is to allow sufficient time for patients in facilities to receive and review the information sheets as well as allow for educational materials to be posted in dialysis facilities.

### **3.9 Data Analysis**

We will examine the effects of a liberal oral nutritional supplement protocol versus the current standard of care in DCI facilities, which consists of administration of oral nutritional supplements only to those patients with low serum albumin levels, even though balance studies show that dialysis procedure associated catabolism still occurs in patients with albumin levels above this threshold. The primary outcome of all-cause mortality will be assessed using a time-to-event model. Hospitalization and infection rates will be assessed in time-to-event models that allow for repeated events.

#### **3.9.1. Sample Size Considerations:**

Given that the study, due to its pragmatic nature, will be relatively inclusive, we anticipate a death rate consistent with the general dialysis population. For incident dialysis patients in 2010, based on USRDS data, the mortality rate peaked at 440 deaths per 1,000 patient years at risk in month two then fell to 201 in month 12. Given that most patients will be prevalent patients and that most patients who are incident will receive nutritional supplements regardless of randomization assignment, we estimate a mortality rate closer to 15-17% and have considered the lower end of this range, in our power calculations to be conservative.

To determine the sample size, many assumptions are needed. Assuming a non-linear median 4 year

survival for hemodialysis patients, we used a two-sided logrank test with an overall sample size of 3351 subjects (1675 in the usual care group and 1676 in the intensive supplement group) followed for 3 years, achieving 80% power at a 2-sided 0.05 significance level to detect a hazard ratio of 0.85 when the usual care group hazard rate is considered 0.173. This power calculation assumes all subjects begin the study together (no accrual periods). The proportion dropping out of the usual care group is 0.05, and the proportion dropping out of the intensive supplement group is also 0.05. Accounting for the cluster randomized design and an intraclass coefficient of 0.01, based on blocking by facility size and region, approximately 5500 patients in 86 facilities of average size of 65 participants will be needed. This sample size is liberal, as, once a facility is randomized to a treatment arm, new patients will continue to initiate dialysis within that facility. Through study completion, patients initiating dialysis in a facility will receive that facility's treatment. Those initiating dialysis in the final nine months of the study will not be included in primary analyses as patients receive nutritional supplements during the first 90 – 120 days of maintenance hemodialysis regardless of facility randomization arm. Factoring in 2 interim analyses using an O'Brien Fleming Test to allocate the alpha over three analyses inflates the sample size by factor of 1.017. Thus, the total sample size is 5597 patients, a small increase that will readily be accounted for with inclusion of incident patients in participating facilities over the first year of the trial.

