The relationship between serum albumin and outcomes may reflect causality, as anorexia and dysgeusia can lead to inadequate protein and calorie intake, resulting in malnutrition and adverse outcomes, particularly in the context of increased nutritional needs that occurs in the catabolic milieu that is characteristic of hemodialysis; however, this relationship may be substantially more complicated since nutritional markers including serum albumin also reflect underlying inflammation or illness burden. In contrast to hypoalbuminemia and weight loss, both of which are associated with poor outcomes, clinical characteristics that suggest better nutrition or nutritional reserve and therefore better ability to cope with the catabolic effects of hemodialysis, such as higher serum creatinine and higher body mass index, are associated with improved survival.

hemodialysis. This is not an insubstantial issue, as mortality rates are extremely high among hemodialysis patients, with approximately 50% dying within three years of initiating kidney replacement therapy. Notably, poor nutritional status and nutrient deficiency are common among patients treated with

As discussed above, while comorbid conditions common in patients treated with hemodialysis are associated with catabolism, the hemodialysis procedure itself also induces a catabolic state. Studies that explored amino acid losses occurring during dialysis are summarized in Table 1 below, reprinted from Lim et al, consistently demonstrate amino acid losses and negative protein balance during the hemodialysis procedure. Importantly, several small studies, including those described in more detail above, demonstrate that oral intradialytic supplement administration early in the dialysis session appears to ameliorate this catabolic state.

Author (Reference)	Isotope	Flux	Pre-HD/HD					Pre-HD/Post-HD			
			B	O	S	D	NB	B	O	S	NB
Lim (11)	 C leucine	μmol/kg per h → Fractional Δ →	118/117 ↓ 1%	17/14 ↓ 18%	101/88 ↓ 13%	14.4 (12%)	-17/-29 ↓ 71%	118/115 ↓ 3%	17/19 ↑ 12%	101/95 ↓ 6%	-17/-19 ↓ 12%
Ikizler (8)	 C leucine	mg/kgFFM per min →	3.4/3.7	0.5/0.4	2.9/2.7	0.61	-0.5/-1.0	3.4/3.8	0.5/0.6	2.9/3.2	-0.5/-0.6
Raj (9)	 C 6 phenylalanine	Fractional Δ → nmol/kg per min →	↑ 9% 0.8/0.7	↓ 19% —	↓ 7% —	(16%) —	↓ 96% —	↑ 11% —	↑ 21% —	↑ 11% —	↓ 20% —

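### Section 3.9.1 says the power calculation used the lower end of 15-17% mortality, but its hazard of 0.173 is mid-range as an annual risk (15.9%) and above the range as a rate; at a 15% annual risk power is about 78%, not 80%

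*Combined protocol and SAP*

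**What the plan says.** All of this is in section 3.9.1 unless noted.

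- **Mortality range.** The plan starts from national registry figures for incident patients: "the mortality rate peaked at 440 deaths per 1,000 patient years at risk in month two", falling to 201 by month 12. It then moves to a lower figure: "Given that most patients will be prevalent patients", and most incident patients will receive supplements in either arm, so it expects 15-17%. It gives no time unit for that range and does not name the arm it applies to.
- **Claim about the range.** The authors "have considered the lower end of this range, in our power calculations to be conservative".
- **Calculation.** A two-sided logrank test at 0.05, with 3351 patients followed for 3 years and no accrual period, has 80% power "to detect a hazard ratio of 0.85 when the usual care group hazard rate is considered 0.173". A 4-year median survival is assumed.
- **Dropout.** "The proportion dropping out of the usual care group is 0.05", and the same in the intensive arm. No time unit is given.
- **Later steps.** An intraclass coefficient of 0.01 with 86 facilities of 65 gives about 5500 patients. A factor of 1.017 for interim analyses gives 5597.
- **Margin.** "This sample size is liberal, as, once a facility is randomized to a treatment arm, new patients will continue to initiate dialysis" in that facility. The step to 5597 is called "a small increase that will readily be accounted for with inclusion of incident patients in participating facilities over the first year of the trial".

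**The concern.** The statement about the lower end and the hazard of 0.173 stand in the same section and do not match. A hazard of 0.173 is not 15% in either unit that the text allows.

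Fewer deaths mean less power, so the lower end of the range is the unfavourable end. A reader of 3.9.1 will take 80% as the power under the least favourable mortality in the planning range and will assume that higher mortality can only add to it. If 0.173 is really a mid-range or higher value, that safety margin in the mortality input does not exist. This matters most if the result is null: section 3.13 plans to tell participants that there is no significant mortality effect in that case, and the weight given to such a result depends in part on how well powered the trial was thought to be.

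**Working it through.** **1. Where 0.173 sits in the range**

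- ln(2)/4 = 0.1733, so 0.173 is the constant hazard implied by the 4-year median.
- As an annual risk: 1 − exp(−0.173) = 15.9%. The midpoint of 15-17% is 16%.
- As a rate: 17.3 per 100 patient-years, above 17.
- Lower end as an annual risk: −ln(1 − 0.15) = 0.1625. Lower end as a rate: 0.15.
- Upper end as an annual risk: −ln(1 − 0.17) = 0.1863. Upper end as a rate: 0.17.

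This step needs no assumption about dropout or about the power formula. Annual risk is the only unit that puts 0.173 inside the range, so it is the better-supported reading. The rate reading has some support, because the registry figures in the same paragraph are per 1,000 patient-years.

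**2. Reproducing the plan's figure**

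Events needed (Schoenfeld): 4 × (1.960 + 0.842)² / (ln 0.85)² = 1,189.

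Probability of an observed death within 3 years, for death hazard h and dropout hazard d: p = h/(h + d) × [1 − exp(−3(h + d))]. With 5% dropout per year, d = −ln(0.95) = 0.0513.

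- Usual care, h = 0.173: p = 0.3778.
- Intensive, h = 0.85 × 0.173 = 0.147: p = 0.3325.
- Mean 0.3551, so N = 1,189/0.3551 = about 3347. The Freedman formula gives 3362. The plan states 3351.

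Other readings of the 5%:

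- Lost at the outset: N about 3287 (Schoenfeld) or 3301 (Freedman), a looser fit.
- Spread over the three years: N about 3196, which does not reproduce 3351.

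Dropout per year fits best and is used below, with loss at the outset shown beside it.

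Cluster step: 1 + 64 × 0.01 = 1.64, and 3351 × 1.64 = 5,496 (stated: about 5500). Interim step: 5,496 × 1.017 = 5,589 (stated: 5597). The factor 1.017 only pays for the interim looks. Working back from 5597 gives 5597/(1.64 × 1.017) = 3,356, so power at 3351 also stands for 5597.

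**3. Power across the range**

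Power = Φ(√events / 2 × |ln 0.85| − 1.960), with N = 3351 and no incident patients beyond 5597:

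| Usual-care hazard | Meaning | Expected deaths, 5% per year | Power, 5% per year | Power, 5% lost at outset |
|---|---|---|---|---|
| 0.173 | value used | 1,190 | 80.0% | 80.8% |
| 0.1625 | 15% annual risk | 1,133 | 78.1% | 78.8% |
| 0.1863 | 17% annual risk | 1,261 | 82.3% | 82.9% |
| 0.15 | 15 per 100 patient-years | 1,062 | 75.4% | 76.2% |
| 0.17 | 17 per 100 patient-years | 1,174 | 79.5% | 80.2% |

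With 5% per year, the Freedman formula gives 79.9%, 77.9% and 75.3% at 0.173, 0.1625 and 0.15.

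**4. The same loss as a detectable effect**

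Solving for the hazard ratio with 80% power at N = 3351 (5% dropout per year) gives 0.8465 at hazard 0.1625 and 0.8418 at 0.15, against the planned 0.85.

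**The case against.** **Incident patients supply a margin.** This is the strongest objection. The plan names the margin, and only about 100 patients of it (5597 − 5500) are used to reach the final size. As an illustration, suppose that 50% to 100% of losses to death and dropout are replaced, entry stops nine months before the end, time 0 is day 90 (section 3.16), and the design effect is recalculated for the larger facilities. With 5% dropout per year and the 1.017 factor, power is then about 80% to 81% at a 15% annual risk and about 77% to 78% at 15 per 100 patient-years. The replacement rate is assumed, because the plan gives none. The point stands that the shortfall may largely disappear, but extra patients do not make a statement about the mortality input true.

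**The range may describe both arms together.** The mean hazard would be (0.173 + 0.147)/2 = 0.160, an annual risk of 14.8%, which is at the lower end. The text does not support this: the range is argued from the general dialysis population and registry rates, and 0.173 is labelled the usual-care hazard. What stands is that the population of the range should be stated.

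**Real mortality may be higher.** A rate of 201 per 1,000 patient-years would give about 84% power. Section 2.1 cites "approximately 50% dying within three years of initiating kidney replacement therapy", a hazard of ln(2)/3 = 0.231, which would give about 88%. But these are incident-patient figures, which the plan itself sets aside, and the claim concerns its own 15-17% range.

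**The effect is small.** This is accepted. On the better-supported reading it is about 2 points, and planned power does not alter the final estimate, interval or test.

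**Conclusion.** The statement that the lower end of 15-17% was used is not correct: 0.173 is mid-range as an annual risk and above the range as a rate. The cost at the true lower end is about 2 points of power on the annual-risk reading and up to 5 on the rate reading. The size of the loss is much the same whether the 5% dropout is per year or at the outset. These figures assume constant hazards, a hazard ratio of 0.85, the plan's design effect and no incident patients beyond 5597. This is a minor correction.

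Three stronger inferences are tempting, and the documents do not support them:

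- *That the 80% or the sample size is miscalculated.* Both reproduce at 0.173.
- *That no rate from 15 to 17 per 100 patient-years reaches 80%.* This holds only with dropout per year. If the 5% is lost at the outset, a rate of 17 gives 80.2%.
- *That the trial is underpowered or must enrol more.* The incident margin is real, though unquantified, and may cover some or all of the loss.

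**What to change.** Change the text of section 3.9.1 only:

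1. Replace the clause about the lower end and conservatism with: *used a usual-care hazard of 0.173 (about 15.9% per year), from an assumed 4-year median survival*.
2. State whether 15-17% is an annual risk or deaths per 100 patient-years, and that it refers to usual care.
3. Add, keeping the unit that applies: *Assuming 5% dropout per year, power is 80% at a hazard of 0.173 and about 78% at a 15% annual risk (about 75% if 15 deaths per 100 patient-years is meant), before any incident patients beyond 5597, whose contribution has not been quantified.*

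If the authors meant the 5% as a loss at the outset, the three figures become 80.8%, 78.8% and 76.2%, and the sentence should say so.

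The cost is a stated power at lower-end mortality that is 2 to 5 points less favourable than the text now implies. Enrolment, analysis and significance thresholds do not change.

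### The primary mortality model leaves out each facility's own pre-randomization death rate, a cheap way to recover part of the 1.64 design effect

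*Combined protocol and SAP*

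**What the plan says.** Section 3.9.1 starts with "overall sample size of 3351 subjects (1675 in the usual care group and 1676 in the intensive supplement group) followed for 3 years". That number is meant to give 80% power, at a two-sided 5% level, against a hazard ratio of 0.85 with a usual-care hazard of 0.173. The section then inflates for clustering: "Accounting for the cluster randomized design and an intraclass coefficient of 0.01, based on blocking by facility size and region". The result is about 5500 patients in 86 facilities averaging 65 each, and 5597 after a factor of 1.017 for interim looks.

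Facility information enters the design in one place, section 3.8: "Facilities will be randomized 1:1 to study arms, blocked by region and facility size (small, medium, large". For the analysis, section 3.9 promises a time-to-event model for mortality and names no covariate. Section 3.16 adds intent-to-treat and a day-90 time origin for incident patients. Multivariable regression appears there only as a secondary analysis, triggered if key facility or patient factors differ between arms. Neither section says how the primary model handles clustering by facility.

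On data, section 3.7 (Outcomes Ascertainment) says that in routine practice "each facility reconciles events, including deaths, hospitalizations, and infections monthly". Section 3.12 says the routine data are held electronically in the MIS. A facility death rate from before randomization is not mentioned as a blocking factor, a covariate or a sample-size input.

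**The concern.** On the plan's own figures, 0.64/1.64 = 39% of the variance of the primary comparison is the excess caused by differences between facilities, and this is what remains after blocking on region and size. With about 86 randomized units, a chance difference between arms in underlying facility mortality matters when the target hazard ratio is 0.85.

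A facility's earlier death rate is a baseline of the outcome itself, at the level where randomization took place. It is fixed before allocation, so the arm cannot influence it. It can also carry local case mix and care patterns that region and size do not. Leaving it out of the primary model gives up precision that needs no more patients. An adjustment triggered by observed imbalance does not recover this, because it is not part of the primary test.

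**Working it through.** **1. Reproduce the plan.** Inputs from 3.9.1: hazard ratio 0.85, hazard 0.173 per year, two-sided alpha 0.05, power 80%, 3 years, no accrual period, and 5% dropout per arm (whether per year or in total is not stated).
- Schoenfeld's formula gives 1189 deaths. With 5% loss per year the mean event probability is 0.3551, so N = 1189/0.3551 = 3348, against 3351 stated.
- Design effect: 1 + (65 - 1) x 0.01 = 1.64. Then 3351 x 1.64 = 5496, stated as about 5500.
- 5500 x 1.017 = 5594, against 5597 stated. The plan's figures reproduce.

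**2. Put the intraclass coefficient on the rate scale.** It inflates a comparison over 3 years, so I apply it to 3-year mortality.
- p = 1 - exp(-3 x 0.173) = 0.405.
- Between-facility variance of p = 0.01 x 0.405 x 0.595 = 0.00241, so the SD is 0.0491.
- dp/dh = 3 x exp(-0.519) = 1.785, so the SD of the facility hazard is 0.0491/1.785 = 0.0275.
- Coefficient of variation = 0.0275/0.173 = 0.159; squared, 0.0253.

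**3. Reliability of a past rate.** Assume a steady census of 65. Expected deaths are D = 65 x 0.173 x years, and the sampling variance of the log rate is about 1/D.
- 1 year: D = 11.2, 1/D = 0.0889, reliability = 0.0253/(0.0253 + 0.0889) = 0.22.
- 3 years: D = 33.7, 1/D = 0.0296, reliability = 0.0253/(0.0253 + 0.0296) = 0.46.

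**4. Design effect and power after adjustment.** Let r be the correlation between a facility's true mortality before and during the trial. The documents give no value; I assume 0.5 to 0.9. The share of between-facility variance removed is q = r² x reliability. The design effect is DE = 1 + 0.64 x (1 - q). Power = Phi(2.8016 x sqrt((5597/1.017/DE)/3351) - 1.96).

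| History | r | q | DE | Power |
|---|---|---|---|---|
| none | - | 0 | 1.64 | 80% |
| 1 year | 0.5 | 0.055 | 1.60 | 81% |
| 1 year | 0.9 | 0.18 | 1.53 | 83% |
| 3 years | 0.5 | 0.115 | 1.57 | 82% |
| 3 years | 0.9 | 0.37 | 1.40 | 86% |

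With three years of history the gain is worth about 3351 x (1.640 - 1.566) = 250 to 3351 x (1.640 - 1.402) = 800 patients. If r were only 0.3, q would be 0.09 x 0.46 = 0.041, DE 1.61 and power just under 81%.

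**5. Cross-check.** A cluster-level ANCOVA uses DE = 1.64 x (1 - R²), where R² = r² x (baseline reliability) x (follow-up reliability). Baseline reliability is 0.205 for 1 year and 0.396 for 3 years; follow-up reliability is 0.396. For r = 0.5 to 0.9 it gives DE 1.61-1.53 with 1 year and 1.58-1.43 with 3 years. The two routes agree closely.

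**The case against.** - **The design meets its target without this.** That is true. The 80% is reached on the plan's inputs, and 3.9.1 expects incident patients to add to the sample. A reader might infer that the sample size is wrong or the trial underpowered; the documents do not support that.
- **The gain may be smaller than it looks.** A reader might apply the 0.01 to one-year mortality of 16%. Reliability would then be 0.40 (1 year) and 0.66 (3 years), the design effect as low as 1.30 and power up to 88%. This does not hold together. A one-year coefficient of 0.01 implies about 0.025 over 3 years and a design effect of 1 + 64 x 0.025 = 2.6, so the starting 1.64 and 80% would no longer apply.
- **The correlation is unknown and may be attenuated.** A crude past rate includes deaths in the first 90 days, which the primary analysis leaves out for incident patients, and it includes patients who would not be eligible or would not agree. Patient turnover is heavy. This stands and is why the range is wide.
- **Section 3.16 partly covers it.** Past mortality could count as a key facility factor. But it is not named, and the adjustment is secondary and conditional.
- **It is late.** Section 3.11 reports the first interim analysis as done, so blocking cannot change, and a revised final model would differ from the one tested at the interim. This also stands. It is eased because the covariate uses only pre-randomization data and 3.11 keeps investigators blinded to interim results.
- **Availability is inferred.** Sections 3.7 and 3.12 make it very likely, but do not say that earlier facility death rates are archived.

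**Conclusion.** The point holds as a cheap efficiency improvement that the plan should take up. It is not an error in the stated sample size. The primary model ignores a facility-level baseline of its own outcome while the design pays a 64% inflation for facility differences.

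The realistic gain is about 2 to 6 percentage points of power with three years of history, and 1 to 3 points with one year. This rests on an intraclass coefficient of 0.01 for 3-year mortality, 65 patients per facility, an assumed between-period correlation of 0.5 to 0.9, and no allowance for unequal facility sizes. A lower correlation would make the gain slight. The gain also presupposes a primary analysis that accounts for clustering, which 3.9 and 3.16 do not yet specify.

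**What to change.** Before the primary data are unblinded, add to 3.16:
- The primary time-to-event model accounts for clustering by facility (shared frailty or cluster-robust variance; name one).
- It includes, as a prespecified covariate, the facility's death rate over one fixed window: the 36 months before its randomization, or all available months if fewer.
- The rate takes a form that is defined when a facility has no deaths, for example an empirical-Bayes or continuity-corrected log rate. Where possible it is computed on the time scale of the analysis population, after day 90 of dialysis.
- The same clustered model without the covariate is reported alongside.
- The text notes that the interim test preceded this change.

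The cost is one MIS extraction for about 86 facilities and a short paragraph. If the correlation proves low, little is gained, and the result without the covariate is still reported.
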